7.3.2 Screening and baseline procedures

Pre-screening prior to informed consent may be done with chart reviews or following standard of care assessments to determine if subjects may be potential candidates for the study. Assessments performed exclusively to determine eligibility for this study would be done only after informed consent has been obtained.

Assessments performed for clinical routine and documented in patient's records may be used for baseline even if they have been done prior to informed consent being obtained.

A screening log will be tracked. Screening failures will be documented.

If the patient enrollment and screening is done at a location separate from the orthotic clinic (e.g. rehabilitation clinic), remote screening including a video of the performance of the BBS will be done at the orthotic clinic to reduce patients' travel efforts to the investigator. Patients must give their informed consent before entering this remote screening procedure.

Two baseline assessments will be performed in order to generate a more confident baseline assessment. Both baseline assessments should be performed within 1 or 2 days. Only the first baseline measurement will be used for statistical analysis.

7.3.2.1 The screening procedures include:

- Informed consent
- Inclusion/Exclusion criteria
- Ability of the patient to sufficiently use C-Brace (via DTO testing)
- Berg Balance Scale
- Demographics: age, gender, ethnicity, weight, height, BMI

ottobock.	CLINICAL INVESTIGATION PLAN	Document number:	PD-PS00120016A-001
		Version number:	7
Project name	Clinical trial comparing C-Brace to KAFO/SCO	Project no.	PS00120016A

- General health information
- Functional muscle test (Janda) / Manual Muscle Testing (MMT)
- Sensitivity test (Rydel-Seiffer Test)
- Passive range of motion assessment (neutral zero method)
- Medical history: Joint replacement, current orthosis use, current use of assistive devices, fall history

7.3.2.2 The first baseline procedures include:

- Review patient's eligibility criteria
- Functional and self-reported baseline assessment (Full assessment of outcome measures)

Performance Assessment

Functional assessment will be done using the Berg Balance Scale, the 6-minute walk test, Dynamic Gait Index, and the Stair Assessment Index. If the first baseline procedure is performed within 24 hours of the screening, the results from the Berg Balance Scale testing, obtained during screening, may be used as first baseline value.

Self – administered Questionnaires:

Activity-specific Balance Confidence Scale, Reintegration to Normal Living index questionnaire, EQ-5D-5L, SF36, Work limitation questionnaire and the OPUS questionnaire. For a detailed description of administered questionnaires, please refer to section 8.2.

Note that screening and first baseline procedures may be combined in one visit.

For statistical analysis, only values from the first baseline will be used. Values from second baseline will be used only to support the values from the first baseline.

7.3.2.3 The second baseline procedures include:

- Functional baseline assessment (Performance assessment)

7.3.2.4 C-Brace potential

Testing C-Brace potential (DTO) with patients is done during screening to ensure the use is appropriate and possible. In the case, a patient cannot fulfill the test criteria; this will be handled as a screening failure.

7.3.3 Randomization

Patients are assigned to treatment groups by means of a state-of-the-art randomization procedure. For details on the randomization procedure, please refer to section 10.3.1.

ottobock.	CLINICAL INVESTIGATION PLAN	Document number:	PD-PS00120016A-001
		Version number:	7
Project name	Clinical trial comparing C-Brace to KAFO/SCO	Project no.	PS00120016A

7.3.4 Fitting and Accommodation

7.3.4.1 KAFO / SCO

Patients entering the study will use their existing fitted KAFO/SCO.

Up to 10 hours of accommodation support with a physical therapist/orthotist will be provided in-house after enrollment within 2 weeks. The progress of accommodation will be assessed and documented. Benchmarks will be used to check patients' ability to use their current orthosis. Two levels will be used for benchmarking:

- Level 1, the minimum requirement for all patients to use their current device should be demonstrated at two different points in time (see 7.3.4.3).
- Level 2 will be documented for patients with higher functional status, walking outdoors, over ground surfaces, steep ramps, slopes and climbing stairs with step-over-step pattern.

7.3.4.2 C-Brace

Up to 10 hours of accommodation support with a physical therapist/orthotist will be provided in-house after definitive fitting within 2 weeks. The progress of accommodation will be assessed and documented. Benchmarks will be used to check patient's readiness to be discharged with C-Brace.

- Level 1, the minimum requirement for all patients to use C-Brace should be demonstrated at two different points in time (see 7.3.4.3).
- Level 2 will be documented for patients with higher functional status, walking outdoors, over ground surfaces, steep ramps, slopes and climbing stairs with step-over-step pattern.

C Brace accommodation support shall follow standardized Ottobock procedures.

7.3.4.3 Benchmarks

Level 1 benchmarking requires independent donning/doffing of the orthosis, charging of the device (if applicable), transfers sit to stand / stand to sit, standing in the orthosis with or without assisted device for a minimum of 2 minutes, safe over ground ambulation, ambulatory turns, to perform a swing phase, walking ramps with a low gradient and climbing stairs with step-to pattern. CPO or physical therapist shall do benchmark assessment.

ottobock.	CLINICAL INVESTIGATION PLAN	Document number:	PD-PS00120016A-001
		Version number:	7
Project name	Clinical trial comparing C-Brace to KAFO/SCO	Project no.	PS00120016A

C-Brace and KAFO/SCO home use may only be permitted after successful Level 1 benchmark testing. C-Brace settings shall be documented by pdf-exports of the cockpit app and device read-out.

Both devices shall be fitted with a step-count transponder. After 14 days, the patient will remove the step-count transponder from the orthosis and will send it back to the study site in a prepared envelope which will be handed to the patient after passing the benchmark criteria (Level 1). After having received the step-count transponder, the site investigator(s) and the sponsor will analyze the daily step count of the patient.

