7.3.5 Home use (both arms) / Follow-up phone calls

Patients will be followed up by phone calls after discharge with KAFO/SCO or C-Brace: End of month 1, end of month 2.

The purpose of these phone calls is to check if any notable adverse events, device malfunctions or falls have occurred. Patients should be reminded during this call on use requirements and on the minimum use time of the device to avoid non- or misuse. The phone call shall follow a detailed procedure (see Annex III), results will be documented in a CRF and shall be conducted by the investigator.

Patient is responsible to call the investigator in the case of malfunction, fall or other limiting event without any further delay.

A patient diary is to be documented by the patient to ensure proper collection of fall information and to bring it at each visit.

7.3.6 Study visit 1

After 3 months of C-Brace or KAFO/SCO home use, respectively, a full performance assessment using clinical tests and questionnaires, as defined in 8.2 will be performed.

During study visit 1, patients will perform the following clinical tests and will fill out the following questionnaires:

Clinical tests

- Berg Balance Scale
- Dynamic Gait Index (DGI)
- Stair Assessment Index (SAI)
- 6-minute walk test

ottobock.	CLINICAL INVESTIGATION PLAN	Document number:	PD-PS00120016A-001
		Version number:	7
Project name	Clinical trial comparing C-Brace to KAFO/SCO	Project no.	PS00120016A

Questionnaires

- Changes in current assistive devices
- Documentation of falls (Analysis of patient diary)
- Documentation of fear of falling
- Activity-specific balance confidence (ABC) Scale
- EQ-5D-5L
- Medical Outcomes Study Short Form (SF-36)
- Orthotics & Prosthetics User Survey (OPUS)
- Quebec User Evaluation of Satisfaction with Assistive Technology (QUEST)
- Reintegration to Normal Living (RNL) Index questionnaire
- Work limitations questionnaires WLQ-25

Device settings and step count shall be read out from C-Brace. An anamnestic interview is conducted to document possible changes in the medical history, specifically the use of assistive devices and to record AE's, SAE's and device malfunctions.

Study visit 1 has to be planned 3 months after patients have passed the benchmarking criteria and have been discharged to use the orthosis. To facilitate the appointments with the patients, a time frame of -1 to +2 weeks around the scheduled visit is allowed.

The following test sequence is recommended:

Test sequence

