7.3.8 Wash out phase

In the arm “C-Brace cross-over to KAFO/SCO”, a wash out phase of 4 weeks is implemented to take a possible carry over effect into account. For safety reasons, wash out phase will begin after patient reaches benchmark level 1.

In the arm KAFO/SCO crossover to C-Brace, no carry over effect is estimated, as it was not observed in previous studies.

7.3.9 Study visit 2

After 3 months of C-Brace or KAFO/SCO home use, full performance assessment using clinical tests and questionnaires, as defined in 8.2 will be performed.

Procedures will follow the description in section 7.3.6 Study visit 1. Two individual questions to evaluate patient-related outcomes (PRO) will also be asked.

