9.3.1 Inclusion criteria

- Patient has been tested with the Trial Tool (DTO) and demonstrated the potential to utilize the C-Brace successfully (see section benchmarks: independent donning/doffing of the orthosis, charging of the device, transfers sit to stand/stand to sit, standing in the orthosis with or without assisted device for a minimum of 2 minutes, safe over ground ambulation, ambulatory turns and to perform a swing phase).
- Patient has a BBS score < 45
- Lower limb functional impairment according to CE label wording
- Prior active and compliant use of unilateral or bilateral KAFO or SCO in the past 3 months prior to enrollment in the study
- Patient meets minimum physical requirements to be fitted with a C-Brace, such as muscle status, joint mobility, leg axis and proper control of the orthosis must be guaranteed.

ottobock.	CLINICAL INVESTIGATION PLAN	Document number:	PD-PS00120016A-001
		Version number:	7
Project name	Clinical trial comparing C-Brace to KAFO/SCO	Project no.	PS00120016A

- The User must fulfill the physical and mental requirements for perceiving optical/acoustic signals and/or mechanical vibrations
- The existing muscle strength of the hip extensors and flexors must permit the controlled swing-through of the limb (compensation using the hip is possible).
- Patient's commitment to use C-Brace 2 at least 1-2 hours per day 5 days per week-
- Patient is ≥ 18 years old
- Patient is willing and able to independently provide informed consent.
- Person is willing to comply with study procedures

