In order to perform a sensitivity analysis, patients who terminated treatment early, will be imputed using multiple imputation methods in order to substitute missing values. Here, multiple copies of the original dataset will be generated by replacing missing values using e.g. a multivariate normal distribution. Each of these complete sets will be analyzed as complete sets and the corresponding parameter and standard error estimates will be combined with taking the uncertainty of the imputation process into account.

For the patients missing follow-up data, proportions of missingness, type of missing measurements, patient characteristics and baseline value levels will be explored in order to detect patterns of missing data. If data is assumed to be missing at random the following imputation strategy will be used.

A linear mixed effects model with the outcome measure as dependent variable will be fitted to the data. This model will use the treatment group and period as fixed factor and the first baseline measure as covariate. Random patient effects will be introduced for the intercepts and thus taking the correlation within patients into account. The analysis implicitly uses a weighted average to estimate the outcome measures, with estimations coming from the complete observations and from the observations with missing values.

Missing data for study patients at follow-up on C-Brace, KAFO/SCO or both because they 1) died, 2) are lost to follow-up (LTFU), 3) withdrew from the study or were withdrawn from the study by the investigator, 4) miss the follow-up visit or 5) do not complete the outcome measure at follow-up, will be imputed by using a mixed model with a random intercept for patient and treatment group as predictor variables.

The details of the imputations methods applied will be documented in the study report.

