10.3 Planned statistical analysis

In general, the most suitable statistical analysis consistent with the form of data will be used and the underlying assumptions of the statistical method will be verified through appropriate pre-tests.

ottobock.	CLINICAL INVESTIGATION PLAN	Document number:	PD-PS00120016A-001
		Version number:	7
Project name	Clinical trial comparing C-Brace to KAFO/SCO	Project no.	PS00120016A

The analysis will be performed on the intention-to-treat (ITT) population and then on the per-protocol (PP) population. The ITT population is defined as all the patients randomized into their randomization group, regardless of the treatment received or their outcome in the study. The PP population is defined as all the patients in the ITT population without any major protocol deviations

For the outcomes measures being evaluated, three assessments are undertaken:

after base line measurements with original orthosis (first baseline measurement)

after first follow up measurement with the C-Brace or original orthosis

after second follow-up measurement with the C-Brace or original orthosis

Quantitative variables will be summarized using standard descriptive statistics (average, standard deviation, median, minimum and maximum, first and third quartile). Qualitative variables will be described using group sizes and frequencies. When relevant, 95%confidence intervals will be given.

Patient characteristics at enrolment will be presented and compared in each group to ensure the groups are initially comparable. The features of any patients lost to follow-up will be studied and influence the imputation strategy as described in 10.2.

Patient profile plots for the outcome measures in both treatment groups for all three assessments will be viewed, showing imputed values. Furthermore, the group means in each treatment group will be evaluated. Outcome measures will be visualized for the crossover periods in scatter plots of first follow up measurement against second follow-up measurement in both treatment groups i.e. period vs period plots.

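### The plan does not say how a patient who never passes Level 1 on C-Brace enters the ITT analysis, and its default imputation would credit that patient with the passers' benefit

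*Combined protocol and SAP*

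**What the plan says.** - **Gate (7.3.4.3).** "C-Brace and KAFO/SCO home use may only be permitted after successful Level 1 benchmark testing". Sections 7.3.4.1 and 7.3.4.2 ask for Level 1 to be shown on two occasions.
- **Visit 1 (7.3.6).** "Study visit 1 has to be planned 3 months after patients have passed the benchmarking criteria and have been discharged to use the orthosis".
- **Visit 2 (7.3.9).** It comes after three months of home use, and "Procedures will follow the description in section 7.3.6 Study visit 1".
- **Schedule (8.3).** BBS is marked at screening, both baselines, the two study visits and the additional COVID-19 visits. It is not marked at C-Brace fitting or at any training/benchmarks row.
- **Analysis set (10.3).** ITT is "all the patients randomized into their randomization group, regardless of the treatment received or their outcome in the study".
- **Missing follow-up (10.2).** The closing list of reasons includes patients who "withdrew from the study or were withdrawn from the study by the investigator" and patients who miss the visit. All are imputed from a mixed model with a random patient intercept and treatment group. The sensitivity analysis is also multiple imputation.
- **Screening (9.3.1).** The trial-orthosis (DTO) test ends its list with "safe over ground ambulation, ambulatory turns and to perform a swing phase". Level 1 goes on to require "walking ramps with a low gradient and climbing stairs with step-to pattern".

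No section says what happens, in conduct or in analysis, to a randomised patient who does not reach Level 1. The paragraph on treatment failures in 7.3.1 covers only poor fit and under-use.

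**The concern.** The confirmatory claim is made for everyone randomised, but the C-Brace BBS is observed only in patients who, after randomisation, proved able to use the device. That selection depends on the response to treatment. A model that learns the C-Brace effect from passers and applies it to non-passers pushes the BBS difference towards C-Brace.

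The gate also applies to KAFO/SCO. Those patients must already be active users of that orthosis, however, so non-attainment should fall mainly on C-Brace and would not cancel between devices. At stake is the size of the reported effect for all randomised patients. No planned analysis shows how the result changes if non-passers gain nothing.

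**Working it through.** **Inputs.** Planning difference Δ = 6.6429 and SD of the difference 4.9085 (10.1.1). Target of 56 randomised (10.1.2). The documents give no Level 1 failure fraction f, so a range of 5% to 30% is assumed.

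**The plan's own target.** The McNemar formula in 10.1.2, with both proportions at 0.1333, one-sided α = 0.05 and power 0.80:

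n = [(1.645 × √0.1333 + 0.842 × √(0.1333 − 0.1333²)) / 0.1333]² = 44.24, and 44.24 / 0.8 = 55.3, rounded up to 56.

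This agrees with the stated 44.2386 and 56.

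**What the mixed model gives a non-passer.** The model in 10.3.2 (treatment, period, first-baseline BBS, random patient intercept) was simulated for 56 patients with C-Brace BBS missing in a fraction f. Assumed settings were a mean BBS of 35 on the own orthosis, a between-patient SD of 6 and 150 replicates.

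- f = 10%: imputed mean benefit of non-passers 6.69, treatment estimate 6.69, mean with non-passers at zero benefit 5.97.
- f = 20%: imputed mean benefit 6.70, treatment estimate 6.66, mean with non-passers at zero benefit 5.34.
- If non-passers also start 5 points lower, their imputed benefit is 7.13 (10%) and 7.32 (20%).

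On average, then, the model gives non-passers at least the passers' benefit. Individual values vary with the patient's own baseline and KAFO/SCO score.

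**Size of the overstatement.** If non-passers gain nothing, the all-randomised mean is (1 − f) × 6.6429 and the overstatement is f × 6.6429.

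| f (assumed) | f × 56 patients | All-randomised mean | Overstatement |
|---|---|---|---|
| 5% | 2.8 | 6.31 | 0.33 |
| 10% | 5.6 | 5.98 | 0.66 |
| 20% | 11.2 | 5.31 | 1.33 |
| 30% | 16.8 | 4.65 | 1.99 |

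**Effect on the test.** Mixing the two groups gives SD = √(4.9085² + f(1 − f) × 6.6429²), which is 5.12, 5.30, 5.58 and 5.78 for the four rows. One-sided paired-t power at n = 56 and α = 0.05 stays at about 1.00 in every row.

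**The case against.** **Section 10.2 is not blind to informative missingness.** It says the method depends on the reason for the missing data, asks for missingness patterns to be explored, and introduces the mixed model for data assumed missing at random. Section 10.3 lets the features of patients lost to follow-up influence the imputation. A reader might infer that the plan always treats such missingness as uninformative; that goes too far. What stands is narrower. No method is given for data not missing at random, the closing list in 10.2 applies the mixed model to withdrawn and missed-visit patients without repeating the condition, and the only stated response to a pattern in the primary measure is that the study may be declared invalid.

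**Screening limits the problem.** A reader might infer that the DTO test lets such patients through freely. It does not: failing it is a screening failure (7.3.2.4), its list covers Level 1 apart from low-gradient ramps and step-to stairs, and up to 10 hours of accommodation follow. Section 16.2 also names lack of proficient use as a reason to stop the study. The group is residual, but it need not be empty.

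**Permanent failure is an inference.** A reader might conclude that a patient who has not passed by day 14 is out of the study or cannot cross over. The documents do not say so; they are silent. That silence is itself the gap.

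**COVID-19 restarts are an exception.** Section 7.3.12 takes a BBS before the Level 1 re-test, but only in interrupted patients, and it is not the three-month value.

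**Conclusion.** The point holds as a gap in the primary analysis. Following the plan as written, a C-Brace non-passer would be imputed at roughly the passers' effect, and no sensitivity analysis departs from missing at random. The overstatement is 0.33 to 1.33 BBS points for f between 5% and 20%. This assumes that non-passers gain nothing, that the planning difference applies to passers, and that non-attainment is recorded as withdrawal or a missed visit. The true f is unknown and could be near zero.

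Two stronger readings are not supported. A reader might infer that the primary result could be overturned; at the planning effect it is very unlikely to be. A reader might also set the all-randomised mean against the 3-point limit in 10.4 and argue that a modest effect would fall below it. Section 10.4 does call a smaller difference clinically irrelevant, but it uses the limit only as an optional interim futility rule on the observed mean change. The confirmatory null in 10.1.1 is a difference of zero or less. On the planning effect the mean would drop below 3 only if f exceeded 1 − 3/6.6429 = 55%.

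**What to change.** **In 10.2:**
- Name non-attainment of Level 1 as a separate missing-data reason, and do not impute it at the passers' C-Brace effect.
- Pre-specify, at least as a sensitivity analysis of the primary endpoint, a no-benefit multiple imputation. Draw the missing C-Brace BBS from the KAFO/SCO follow-up distribution, given the patient's own KAFO/SCO BBS and first baseline. A single first-baseline value is not a good substitute. It ignores imputation uncertainty, and it would score a negative effect if KAFO/SCO scores rise after the accommodation training that follows baseline.
- Report the number of non-passers by device and sequence.

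**In 7.3.4.3 and the schedule (8.3):** where the site judges it safe, record a supervised in-clinic BBS on the assigned device at the end of accommodation. The scale can register weak performance, since 8.2.1 deducts points for supervision or assistance. Treat this score as supportive, because it reflects about two weeks of use and not three months. Keep collecting the BBS on the other device.

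How patients who do not pass Level 1 are managed, and whether and when they cross over, is for the sponsor to reconcile across 7.3.4.3, 7.3.6 and 7.3.7.

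**Cost:** a small amount of extra analysis, one extra BBS in a few patients, and a slightly less favourable estimate.

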7.1 Experimental plan

After obtaining informed consent, patients will be screened. Patients fulfilling inclusion/exclusion criteria will be enrolled in the study. After screening, a first baseline assessment will be conducted. Within maximum 48 hours, a second set of baseline data will be collected. Afterwards the participants will be randomly assigned to be fitted either with C-Brace or maintain his/her KAFO/SCO. The randomization procedure will be concealed and assigned off-site. After fitting, an accommodation period follows that will last up to 14 days prior home use. The first follow-up data collection will occur after 3 months after the initial home use period. Afterwards, the patients will cross over to KAFO/SCO or C-Brace, respectively. The participants who were fitted with C-Brace will cross over to KAFO/SCO and vice versa. Another accommodation phase will be offered for both C-Brace and KAFO/SCO wearers to ensure that the patient can properly use both devices before the cross-over home use period. The second follow-up data collection will occur after 3-months of home use. At the end of the study, the patients can choose to keep C-Brace until reimbursement or return to their original KAFO/SCO.

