8.2.2.4 Device Read Outs

- Setup App:

A pdf-export and storage of the data file will be done at definitive fitting, every time a change in the settings is done and at the follow up visits.

- Step Count

A step count transponder will be fixed on C-Brace and on KAFO/SCO before starting the home use phase. It will be read out after each observational period (14 days).

For details on the procedures, please refer to section 23.1 (Appendix I).

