C-Brace is a CE-marked class I medical device. Risk analysis has been conducted and identified risks such as blocking of flexion in knee joints when descending stairs or ramps, unintentional locking during sitting, flexion resistance is not reduced when walking on level ground (swing phase), insufficient extension of knee joint in the stance phase, insufficient extension of the orthosis during standing up. All those identified risk could lead to a fall. After implementation of appropriate measures, the risk analysis concluded that the remaining risks are either acceptable or ALARP (as low as reasonably practicable).

In this clinical study, patients will be randomly assigned to two treatment groups. Treatment group 1 will start with 3 months usage of the patients' KAFO or SCO. The patients will then move to a 3-month period of C-Brace use. Treatment group 2 will start with 3 months of C-Brace use and will then enter into a 4-week washout period before moving to a 3-month period of KAFO/SCO use. This randomization will not add any additional risks to the patients since both groups will use both devices for the same period.

Patients enrolled in the study will enter with their current orthosis (KAFO/SCO). Before performing the clinical tests, patients will receive up to 10h of accommodation training and will be benchmarked according to their ability to use their orthosis. When entering the C-Brace group, patients will again receive up to 10h of accommodation support and an assessment. Patients enrolled in the study who will start with C-Brace, will receive accommodation support and assessment. When switching back to their regular orthosis (KAFO/SCO) they will again receive accommodation and assessment. Therefore, the risks due to switching of the devices in the clinical study are mitigated.

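### In the C-Brace-first sequence, the scheduled 14-day KAFO/SCO step count falls wholly inside the 4-week washout and not in KAFO/SCO home use

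*Combined protocol and SAP*

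**What the plan says.** Four places together fix the timing of the step count.

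- **Start.** Footnote 2 of the study schedule (8.3) has the StepWatch attached once the training benchmarks are met, and the table marks it in both Training/benchmarks rows. Section 8.2.2.4 words the start differently: "A step count transponder will be fixed on C-Brace and on KAFO/SCO before starting the home use phase".
- **Stop.** Section 7.3.4.3: "After 14 days, the patient will remove the step-count transponder from the orthosis and will send it back to the study site". The return envelope is handed over when Level 1 is passed. Section 8.2.2.4 also gives the observation as 14 days.
- **Washout.** Section 7.3.8 provides that, in the C-Brace-to-KAFO/SCO arm only, "a wash out phase of 4 weeks is implemented to take a possible carry over effect into account". On its start: "For safety reasons, wash out phase will begin after patient reaches benchmark level 1".
- **Order.** Section 11 describes this group as having a "4-week washout period before moving to a 3-month period of KAFO/SCO use". Section 8.2.1 gives the same order for the primary endpoint. Section 7.3.12 also separates the two phases: a patient interrupted by lockdown during the washout goes on to the home-use phase that follows it.

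Where there is no washout, home use starts at the benchmark. Section 7.3.6: "Study visit 1 has to be planned 3 months after patients have passed the benchmarking criteria".

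**The concern.** The washout exists so that KAFO/SCO data are not taken while C-Brace use may still be having an effect. The Berg Balance Scale, the other performance tests and the questionnaires respect this, because they are taken after the washout and a further 3 months. The transponder count does not. Its only KAFO/SCO record in this sequence is made during the weeks that the plan itself sets aside for possible carry-over. The other sequence records the same device in home use, with no C-Brace exposure beforehand apart from the screening test.

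Usage habits on the two devices are a secondary objective (6.1.2), and section 7.3.4.3 commits the site and the sponsor to analysing daily steps. If the counts are compared between devices, the KAFO/SCO side mixes two phases, split exactly by sequence.

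**Working it through.** The plan states no figure for this point, so there is none to reproduce. The check is an overlap of intervals.

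**Inputs**, in days from passing Level 1 (day 0):

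- Step count: 0 to 14 (8.3 footnote 2; 7.3.4.3).
- Washout, C-Brace-first sequence only: 0 to 28 (7.3.8).
- Home use: 28 to 119 after a washout, otherwise 0 to 91. Three months is taken as 91 days (assumption). The visit window of -1 to +2 weeks in 7.3.6 gives 84 to 105 days.

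**Formula.** Overlap of [a, b] with [c, d] = max(0, min(b, d) − max(a, c)).

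**KAFO/SCO count, C-Brace-first sequence:**

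- With the washout: min(14, 28) − max(0, 0) = 14 days.
- With home use: max(0, min(14, 119) − max(0, 28)) = max(0, −14) = 0 days.

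**Each of the other three counts:**

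- With home use: min(14, 91) − max(0, 0) = 14 days.

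| Sequence | Device | Days in washout | Days in home use | Days from end of count to visit |
|---|---|---|---|---|
| KAFO/SCO first | KAFO/SCO | 0 | 14 | 91 − 14 = 77 |
| KAFO/SCO first | C-Brace | 0 | 14 | 77 |
| C-Brace first | C-Brace | 0 | 14 | 77 |
| C-Brace first | KAFO/SCO | 14 | 0 | 119 − 14 = 105 |

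**Other reading of 8.2.2.4.** If the sensor were fixed at the end of the washout, the count would run from day 28 to day 42. Overlap with the washout is max(0, 28 − 28) = 0, and with home use 42 − 28 = 14. The fourth row would then match the other three.

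**Patients affected.** With 1:1 sequences (assumption), 56 / 2 = 28. If the planned 20% dropout all fell before the second recording, 28 × 0.8 = 22.4, so about 22.

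**Effect on a device comparison.** Let δ be the amount by which a KAFO/SCO count in the washout differs from one in home use. The mean C-Brace minus KAFO/SCO difference is D in the KAFO/SCO-first sequence and D − δ in the other. Averaging the two sequences equally gives D − δ/2. The documents give no value or sign for δ, so the size and direction of the bias are unknown.

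**The case against.** The strongest reply is that section 8.2.2.4 requires only that the sensor be in place before home use, which a site could take to mean the end of the washout. The wording allows that. However, fixing the sensor at Level 1 satisfies the same sentence, and the schedule and the envelope hand-over both point to the benchmark. After the second training row the schedule lists only two phone calls and Study visit 2, COVID-19 restarts aside, so no visit exists at which to fit a sensor when the washout ends. If sites do read it differently, the timing will vary between sites, which also needs correcting.

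The reply is right to limit the point. Three stronger conclusions are tempting, and the documents do not support them.

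- A reader might infer that the step counts miss home use altogether. Three of the four counts lie wholly inside it, although they cover only its first 14/91 = 15% (13.3% to 16.7% over the visit window).
- A reader might infer that C-Brace is recorded from the first day on an unfamiliar device. Recording follows fitting, Level 1 shown at two time points and, in section 7.1, this: "After fitting, an accommodation period follows that will last up to 14 days prior home use".
- A reader might infer that nothing is known of C-Brace steps later on. Section 7.3.6 and Appendix I read steps from the joint unit at the study visits. What is missing is a matching KAFO/SCO log.

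It is also true that section 10 never names step count, that all secondary inference is exploratory, and that the phone protocol in Appendix III asks about wear time for both devices. Wear time does bear on usage habits, but it is self-reported and is not a step count.

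**Conclusion.** The point holds for one of the four sequence-by-device counts. In the C-Brace-first sequence, 14 of 14 KAFO/SCO recording days fall in the washout, in about 28 of 56 patients (about 22 under the dropout case above). The KAFO/SCO transponder count is thus exposed to possible C-Brace carry-over in one sequence only, and a pooled device difference would absorb half of any resulting shift. COVID-19 restarts add a further inconsistency: under section 7.3.12, a patient interrupted in the washout gets a StepWatch on restart and is recorded in home use, so the same sequence can be sampled in two phases.

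This rests on the sensor being fitted at the benchmark, as footnote 2 indicates, and on 1:1 sequences. The importance is modest. The measure is an exploratory read-out without an analysis of its own, and the primary Berg Balance Scale analysis is untouched. The correction is worth making because it is cheap and because the transponder is the only step count available on both devices.

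**What to change.** Reconcile sections 7.3.4.3, 7.3.8, 8.2.2.4 and footnote 2 of 8.3 so that, in the C-Brace-first sequence, the 14-day KAFO/SCO recording starts at the end of the washout. It then covers the first 14 days of home use, as the other three counts do. State in 8.2.2.4 or section 10 that the device comparison uses the transponder count from that window, and that the C-Brace internal log is descriptive for C-Brace only. Report counts already recorded in the washout separately.

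The sensor and the recording length stay the same, and no visit is added. The sensor would be handed out at the benchmark visit or mailed, and the patient would attach it when the washout ends, prompted by a phone reminder. The price is some risk of wrong placement or lost data, which attachment by staff at the benchmark visit avoids.

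Recording the last 14 days before each study visit would bring the counts closer to the 3-month assessments. That is an optional design choice and is not needed to resolve this point.
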